4 INTRODUCTION

This statistical analysis plan (SAP) is based on the most recent approved clinical study protocol (CSP), the most recent approved electronic case report form (eCRF), and the most recent approved eCRF completion guidelines.

This SAP (Methods) documents the planned statistical analyses of efficacy and safety endpoints defined in the VX19-445-116 study protocol. [REDACTED]

The Vertex Biometrics Department will perform the statistical analysis of efficacy and safety data; SAS (Version 9.4 or higher) will be used to generate all statistical outputs (tables, figures, listings, and datasets). The SAP will be finalized and approved prior to the clinical database lock and treatment unblinding for the study. Any revisions to the approved SAP will be documented and approved in an amendment prior to the clinical database lock and treatment unblinding. Any changes made to the SAP (Methods) after the clinical database lock has occurred will be documented in the clinical study report for this study.

5 STUDY OBJECTIVES

5.1 Primary Objective

To evaluate the efficacy of elxacaftor/tezacaftor/ivacaftor (ELX/TEZ/IVA) in subjects 6 through 11 years of age with cystic fibrosis (CF), heterozygous for *F508del* and a minimal function (MF) mutation (F/MF).

5.2 Secondary Objectives

- To evaluate the pharmacodynamics (PD) of ELX/TEZ/IVA
- To evaluate the safety of ELX/TEZ/IVA

6 STUDY ENDPOINTS

6.1 Primary Endpoint

- Absolute change in lung clearance index_{2.5} (LCI_{2.5}) from baseline through Week 24

6.2 Secondary Endpoints

[figure not shown]
- Absolute change in sweat chloride (SwCl) from baseline through Week 24
- Safety and tolerability assessments based on adverse events (AEs), clinical laboratory values, standard 12-lead electrocardiograms (ECGs), vital signs, pulse oximetry

7 STUDY DESIGN

7.1 Overall Design

This is a Phase 3b, randomized, double-blind, placebo-controlled, parallel-group, multicenter study in CF subjects aged 6 through 11 years who are heterozygous for the *F508del* mutation and a minimal function mutation (F/MF genotypes), as shown in Figure 7-1.

Figure 7-1 VX19-445-116 Study Design

ELX: elxacaftor; IVA: ivacaftor; N: number of subjects; TEZ: tezacaftor

^a The Safety Follow-up Visit is scheduled to occur 28 days (± 7 days) after the last dose.

^b Subjects who complete the visits in the Treatment Period, regardless of whether they are on a treatment interruption, will be offered the opportunity to enroll in an optional open-label extension safety study evaluating ELX/TEZ/IVA. The Safety Follow-up Visit is not required for subjects who complete the Week 24 Visit and have enrolled in an open-label study within 28 days after the last dose of study drug.

Approximately 108 subjects are planned to be randomized (1:1) to the ELX/TEZ/IVA group or the placebo group. Randomization will be stratified by $LCI_{2.5}$ determined at the Screening Visit (<10 versus ≥ 10) and weight at the Screening Visit (<30 kg versus ≥ 30 kg).

The planned dosages to be evaluated are shown in Table 7-1.

Table 7-1 Treatment Period Groups and Dosages

Treatment Group	ELX Dosage	TEZ Dosage	IVA Dosage
ELX/TEZ/IVA			
<30 kg	100 mg qd	50 mg qd	75 mg q12h
≥ 30 kg	200 mg qd	100 mg qd	150 mg q12h
Placebo	0 mg	0 mg	0 mg

ELX: elxacaftor; IVA: ivacaftor; q12h: every 12 hours; qd: once daily; TEZ: tezacaftor

7.2 Sample Size and Power

Assuming a within-group SD of 1.5 and a treatment difference of -1.0 between ELX/TEZ/IVA and placebo, a sample size of 49 subjects completing the Treatment Period in each group for a total of 98 subjects will have approximately 90% power for the $LCI_{2.5}$ hypothesis testing, based on a 2-sided 2-sample t-test at a significance level of 0.05. Assuming a 10% dropout rate, approximately 108 subjects will be enrolled.

All power calculations were based on EAST software Version 6.4.

7.3 Randomization

Randomization will be stratified by $LCI_{2.5}$ determined at the Screening Visit (<10 versus ≥ 10) and weight at the Screening Visit (<30 kg versus ≥ 30 kg).

Randomization will occur before the first dose of study drug during the Treatment Period and may occur on either Day 1 or Day -1.

7.4 Blinding and Unblinding

Refer to the CSP Section 10.7 for details.

8 ANALYSIS SETS

The following analysis sets are defined: All Subjects Set, Full Analysis Set (FAS), and Safety Set.

8.1 All Subjects Set

The **All Subjects Set** will include all subjects who are randomized or receive at least 1 dose of study drug. This analysis set will be used for all individual subject data listings and disposition summary tables, unless otherwise specified.

8.2 Full Analysis Set

The **FAS** will include all randomized subjects who carry the intended *CFTR* allele mutation and receive at least 1 dose of study drug. The FAS will be used to summarize subject demographics and baseline characteristics, and for all efficacy analyses in which subjects will be analyzed according to their randomized treatment group, unless otherwise specified.

8.3 Safety Set

The **Safety Set** will include all subjects who receive at least 1 dose of study drug. This safety set will be used for all safety analyses in which subjects will be analyzed according to the treatment they receive, unless otherwise specified.

9 STATISTICAL ANALYSIS

9.1 General Considerations

Continuous variables will be summarized using the following descriptive summary statistics: the number of subjects (n), mean, SD, median, minimum value (min), and maximum value (max).

Categorical variables will be summarized using counts and percentages.

Baseline value, unless otherwise specified, will be defined as the most recent non-missing measurement (scheduled or unscheduled) collected before the first dose of study drug in the Treatment Period.

Absolute change from baseline will be calculated as post-baseline value – baseline value.

Relative change from baseline will be calculated as (post-baseline value – baseline value)/baseline value.

Treatment-emergent (TE) Period will include the time from the first dose date of study drug to 28 days after the last dose of the study drug or to the date of completion of study participation, whichever occurs first.

Unscheduled visits: Unscheduled visit measurements will be included in analysis as follows:

- 1) In scheduled visit windows per specified visit windowing rules
- 2) In the derivation of baseline and last on-treatment measurements
- 3) In the derivation of maximum and minimum values during TE period, and maximum and minimum change from baseline values during TE period for safety analyses
- 4) In individual subject data listings as appropriate

Visit windowing rules: The analysis visit windows for protocol-defined visits are provided in [Appendix A](#).

Incomplete/missing data will not be imputed, unless specified otherwise.

Outliers: No formal statistical analyses will be performed to detect or remedy the presence of statistical outliers, unless specified otherwise.

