9.8.1 Liver Function Tests

The central laboratory will notify the medical monitor of ALT or AST $>3 \times \text{ULN}$ and total bilirubin $>2 \times \text{ULN}$ that are derived from centrally submitted samples.

Subjects with new treatment-emergent ALT or AST elevations of $>3 \times \text{ULN}$, with or without total bilirubin $>2 \times \text{ULN}$, must be followed closely, including confirmatory testing performed by the central laboratory within 48 to 72 hours of the initial finding and subsequent close monitoring of ALT, AST, and bilirubin levels, as clinically indicated.

If a subject cannot return to the site for confirmatory testing, a local laboratory may be used. Local laboratory results must be reported immediately to the medical monitor, and the subject must have the tests repeated and sent to the central laboratory as soon as possible (ideally within 48 to 72 hours).

Study drug administration **must be interrupted** immediately (prior to confirmatory testing) if any of the following criteria are met:

- ALT or AST $>8 \times \text{ULN}$
- ALT or AST $>5 \times \text{ULN}$ for more than 2 weeks

- ALT or AST $>3 \times$ ULN, in association with total bilirubin $>2 \times$ ULN and/or clinical jaundice

A thorough investigation of potential causes should be conducted, and the subject should be followed closely for clinical progression.

Study drug administration **must be discontinued** if the following criterion is met:

- Subsequent ALT or AST values confirm the initial elevation that satisfied the interruption rule (above), and no convincing alternative etiology (e.g., acetaminophen use, viral hepatitis, alcohol ingestion) is identified, regardless of whether transaminase levels have improved.

All subjects in whom treatment is discontinued for elevated transaminases (and bilirubin, as applicable) should have these levels monitored closely until levels normalize or return to baseline.

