9.4.2 Clinical Laboratory

For the treatment-emergent laboratory measurements, the observed values and change from baseline values of the continuous hematology, serum chemistry, and coagulation results will be summarized in SI units by treatment group at each visit.

The number and percentage of subjects meeting at least 1 threshold analysis criterion, during the TE period, will be summarized by treatment group. The threshold analysis of shift from baseline will also be summarized for LFT laboratory parameters. The threshold analysis criteria are provided in [Appendix E](#).

For selected LFT laboratory tests (alanine transaminase [ALT], aspartate transaminase [AST], alkaline phosphatase [ALP], and total bilirubin), a scatter plot of the maximum treatment-emergent value versus the baseline value corresponding to \times ULN (upper limit of normal) will be presented by treatment group. Further, a scatter plot of the maximum treatment-emergent value of ALT and AST, separately, versus the maximum treatment-emergent value of total bilirubin corresponding to \times ULN will also be presented by treatment group.

Results of urinalysis and positive urine/serum pregnancy test will be listed in individual subject data listings only. For positive serum pregnancy listing, subjects with serum HCG which are abnormally high will be selected.

In addition, a listing containing individual subject hematology, chemistry, and coagulation values will be provided. This listing will include data from both scheduled and unscheduled visits.

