12 LIST OF APPENDICES

Appendix A: Analysis Visit Windows for Safety and Efficacy Assessment

Table 12-1 Analysis Visit Windows for Safety and Efficacy Assessments			
Assessment	Visit¹	Target Study Day	Analysis Visit Window (in study days)^{2, 3, 4, 5}
Safety Assessment			
Serum Chemistry Hematology	Day 1 (Baseline)	1	≤1 Pre-dose
	Day 15	15	[1, 22]
	Week 4	29	(22, 43]
	Week 8	57	(43, 85]
	Week 16	113	(85, 141]
	Week 24	169	(141, 183]
	Safety Follow-up	Not applicable	Use nominal visit
Standard 12-lead ECG	Day 1 (Baseline)	1	≤1 Pre-dose
	Week 8	57	[1, 85]
	Week 16	113	(85, 141]
	Week 24	169	(141, 183]
	Safety Follow-up	Not applicable	Use nominal visit
Vital signs (excluding BMI, Weight and Height, and their z-scores) and pulse oximetry	Day 1 (Baseline)	1	≤1
	Day 15	15	[1, 22]
	Week 4	29	(22, 43]
	Week 8	57	(43, 85]
	Week 16	113	(85, 141]
	Week 24	169	(141, 183]
	Safety Follow-up	Not applicable	Use nominal visit
Coagulation	Day 1 (Baseline)	1	≤1 Pre-dose
	Week 24	169	[1, 183]
BMI, Weight, Height and the corresponding z-scores	Day 1 (Baseline)	1	≤1
	Day 15	15	(1, 22]
	Week 4	29	(22, 43]
	Week 8	57	(43, 85]
	Week 16	113	(85, 141]
	Week 24	169	(141, 183]
	Safety Follow-up	Not applicable	>183
Efficacy Assessment and Pharmacodynamic Assessment			

Table 12-1 Analysis Visit Windows for Safety and Efficacy Assessments			
Assessment	Visit¹	Target Study Day	Analysis Visit Window (in study days)^{2, 3, 4, 5}
Sweat Chloride Lung Clearance Index (LCI)	Day 1 (Baseline)	1	≤1 Pre-dose
	Day 15	15	(1, 22]
	Week 4	29	(22, 43]
	Week 8	57	(43, 85]
	Week 16	113	(85, 141]
	Week 24	169	(141, 183]

¹ Visit name for analysis purpose is used to report data in tables and figures.

² The analysis visit windows will be applied using the following rules for both scheduled and unscheduled visits:

- a. If no numerical measurement is available within a visit window, the measurement will be considered missing for the visit.
- b. If there is more than 1 numerical measurement available within a visit window, use the following rules:
 - i. The measurement closest to the target day will be used; or
 - ii. If there are multiple measurements with the same distance from the target day, the latest measurement will be used. If the latest measurement cannot be determined, then unscheduled visit will be selected

³ For measurements collected on the date of first dose of study drug, if it cannot be determined whether the measurement is before or after the first dose:

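### The SAP's visit-window rule gives a scheduled laboratory value no precedence, so a high ALT or AST can be replaced by its own retest in the descriptive by-visit tables

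*SAP*

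**What the plan says.** SAP 9.1 (Unscheduled visits, item 1) admits unscheduled measurements "In scheduled visit windows per specified visit windowing rules". The operative rule is footnote 2 to Table 12-1 in SAP Appendix A: "The analysis visit windows will be applied using the following rules for both scheduled and unscheduled visits". Where a window holds more than one value, footnote 2b gives the order: "The measurement closest to the target day will be used; or", failing which "If there are multiple measurements with the same distance from the target day, the latest measurement will be used". Neither place ranks a scheduled value above an unscheduled one.

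Protocol 9.8.1 requires, for a new treatment-emergent ALT or AST above 3×ULN, "confirmatory testing performed by the central laboratory within 48 to 72 hours of the initial finding". For some of these elevations it also requires study drug to be interrupted before that test.

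Under SAP 9.4.2, observed laboratory values and changes from baseline "will be summarized in SI units by treatment group at each visit". The corresponding protocol text (12.3.4.2) refers to scheduled visits. SAP 9.1 lists mean, median, minimum and maximum among the summary statistics. Item 3 of its unscheduled-visit rules separately keeps unscheduled values "In the derivation of maximum and minimum values during TE period, and maximum and minimum change from baseline values during TE period for safety analyses".

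**The concern.** A confirmatory ALT/AST test exists only because the first value was high. If the scheduled draw was taken before its target day, the retest a few days later may be nearer to target, or equally near, and the rule then selects it. The choice of value in the by-visit table thus depends on the result itself.

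There are two reasons to expect the replacing value to be lower on average. A value selected for being extreme tends to regress toward the mean. For elevations that meet the interruption rule, the retest also follows interruption of drug. If so, the by-visit mean is pulled down, more in the arm with more elevations, and the by-visit maximum can omit the peak. Elevated transaminases are an adverse event of special interest (SAP 9.4.1.1), so the placebo-controlled time course should not turn on whether a child came two days early or two days late.

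**Working it through.** The documents state no replacement rate, so there is no figure of the plan's own to reproduce.

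**Inputs**
- Visit tolerance: ±3 days at Day 15; ±5 days at Weeks 4, 8, 16 and 24 (Protocol Table 3-2).
- Target days 15, 29, 57, 113 and 169, with windows ending at days 22, 43, 85, 141 and 183 (SAP Table 12-1, serum chemistry).
- Retest lag k: 2 or 3 days if the 48–72 hours run from the blood draw. Protocol 9.8.1 counts from when the elevation is first found, so 3 to 5 days after the draw is also tried (assumption).
- Distribution of actual visit days within tolerance: not given (assumption, varied below).

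**Step 1: do both values fall in one window?** Take the latest in-tolerance visit plus 3 days: 18+3=21 (limit 22), 34+3=37 (43), 62+3=65 (85), 118+3=121 (141), 174+3=177 (183). They do at every visit.

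**Step 2: when does the retest win?** With the scheduled draw at offset d from target and the retest at d+k, the retest is used if |d+k| ≤ |d|, that is, if d ≤ −k/2. With all in-tolerance days equally likely:

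| Lag from draw | ±5-day visits | Day 15 (±3) | Five visits pooled |
|---|---|---|---|
| 2 days | 5/11 = 45% | 3/7 = 43% | (4×5/11 + 3/7)/5 = 0.449 |
| 3 days | 4/11 = 36% | 2/7 = 29% | (4×4/11 + 2/7)/5 = 0.348 |

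The average of the two pooled figures is 0.40.

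**Step 3: other assumptions** (pooled over the five visits, averaged over the lags shown):

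| Visit days | Lag 2–3 days | Lag 3–5 days |
|---|---|---|
| Uniform | 40% | 31% |
| Triangular about target | 33% | 22% |
| Normal, SD 2 days | 31% | 18% |
| On-target or late days twice as likely as early days | 26% | 20% |
| Normal, SD 1 day | 18% | 4% |

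The range is about 4–40%, with 40% at the top.

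Week 24 needs a further allowance. For a child entering the extension study within 28 days, participation ends at the Week 24 Visit (Protocol 9.1.6), and so does the treatment-emergent period (SAP 9.1). A later retest should not enter a treatment-emergent summary. If Week 24 is set to zero for all children, the uniform figures become (3×5/11 + 3/7)/5 = 0.358 and (3×4/11 + 2/7)/5 = 0.275, averaging 0.32.

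**Step 4: shift in a by-visit mean.** Shift = share of children with a trigger at the visit × probability of replacement × mean fall at retest. All three inputs are assumed.
- Low: 0.02 × 0.20 × 0.5×ULN = 0.002×ULN.
- High: 0.10 × 0.41 × 2×ULN = 0.08×ULN.
- With replacement at 4%, the low case would be 0.02 × 0.04 × 0.5 = 0.0004×ULN.

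**Step 5: other statistics.** Suppose, for illustration, that 3 of 54 children move from 6 to 3.5×ULN while the rest sit near 0.7×ULN. Both values are far above the median, so it does not move. The by-visit maximum can change, because it may rest on a single child.

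**The case against.** The strongest reply is that little of consequence is exposed. Safety analysis is descriptive, without testing (SAP 9.4). Threshold counts over the treatment-emergent period, scatter plots of maximum values and the full laboratory listing all retain the triggering value (SAP 9.1 item 3, SAP 9.4.2). By-visit and peak-based outputs differ by design and still would after the fix. All of this stands, and it sets the weight of the point.

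A reader might infer several stronger things that the documents do not support.
- **Replacement in 4 of 10 cases as a fact.** That needs uniform visit days and a lag counted from the draw. Samples go to a central laboratory and the protocol counts from the finding, so a longer lag and a lower rate are quite possible.
- **Liver tables shown to be biased low.** The direction is an expectation. A rising ALT would be replaced by a higher value, and mandatory interruption covers only part of the elevations above 3×ULN.
- **Bias in medians or bilirubin.** Medians are essentially unaffected. The retest is triggered by ALT or AST with or without raised bilirubin, so bilirubin is not generally selected for being high.
- **Bias in LCI2.5 or sweat chloride.** The same footnote applies, but neither has an outcome-triggered retest. The sponsor's study team sees neither result after the first dose, and post-screening sweat chloride is withheld from sites (Protocol 10.7.1). The COVID-19 addendum's unscheduled visits are for assessments that were not collected, so they usually displace nothing.

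What remains is the mechanism itself, which follows directly from footnote 2b and Protocol 9.8.1.

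**Conclusion.** The concern holds as a minor weakness in the windowing rule, confined to descriptive by-visit ALT and AST means and maxima. That the selection depends on the outcome follows from the text. The downward direction is reasoned, not documented. Replacement affects up to about 40% of scheduled elevations that trigger a retest, with a plausible range of about 4–40%; the effect on a visit mean is roughly 0.002–0.08×ULN. Both ranges rest on assumptions about visit timing, retest lag, frequency of elevations and fall at retest that the documents do not give. It would be wrong to conclude that the liver safety signal is lost or that any efficacy or pharmacodynamic result is affected. This is a cheap improvement that the trial's conclusions do not depend on.

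**What to change.** In SAP Appendix A, Table 12-1 footnote 2b, add that for by-visit laboratory safety summaries the scheduled-visit value is used when one exists in the window, and otherwise the unscheduled value nearest to target. Cross-refer to this from SAP 9.1, item 1. Unscheduled values stay in the treatment-emergent maximum and minimum, threshold and listing outputs, and they still fill visits missed because of COVID-19. The final tie clause in footnote 2b, which favours the unscheduled visit, need not change for this purpose: it applies only when the later measurement cannot be identified, and a retest dated days afterwards never reaches it.

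Replacement of a scheduled value by its retest then falls to 0% at every visit, the peak-based outputs are unchanged, and the summaries match the protocol's scheduled-visit wording. The cost is one sentence and a small programming change. The downside is that a scheduled value far from target would be preferred to a nearer unscheduled one, and some windows are wide (Week 16 runs from after day 85 to day 141, target 113).

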9.2 Background Characteristics

9.2.1 Subject Disposition

A disposition table will be provided with the number of subjects in:

- All Subjects Set
- Randomized
- Randomized but not dosed
- Full Analysis Set
- Safety Set

The number and percentage (based on FAS) of subjects in each of the following disposition categories will be summarized by treatment group and overall:

- Completed treatment
- Prematurely discontinued treatment and the reason for discontinuation
- Completed study
- Prematurely discontinued the study and the reason for discontinuation
- Rollover to the open-label study

A listing will be provided for subjects who discontinued treatment or who discontinued study with reasons for discontinuation.

9.2.2 Demographics and Baseline Characteristics

Demographics and baseline characteristics will be summarized based on the FAS and presented by treatment group and overall.

Demographic data will include the following:

- Age at baseline (in years)
- Sex (female and male)
- Ethnicity (Hispanic or Latino, not Hispanic or Latino, and not collected per local regulations)
- Race (White, Black or African American, Asian, American Indian or Alaska Native, Native Hawaiian or Other Pacific Islander, Other, and not collected per local regulations)
- Country

Baseline characteristics will include the following:

[figure not shown]
- Weight (kg)
- Weight z-score
- Height (cm)
- Height z-score
- BMI (kg/m²)
- BMI z-score

Stratification categories will include the following:

- LCI_{2.5} at the Screening Visit (<10 versus ≥10)
- Weight at the Screening Visit (<30 kg, and ≥30 kg)

Disease characteristics will include the following:

- LCI_{2.5} at baseline (continuous)
- SwCl at baseline (continuous)

- 
- Prior use of dornase alfa (Yes, No)
 - Prior use of azithromycin (Yes, No)
 - Prior use of inhaled antibiotic (Yes, No)
 - Prior use of any bronchodilator (Yes, No)
 - Prior use of any inhaled bronchodilator (Yes, No)
 - Prior use of any inhaled hypertonic saline (Yes, No)
 - Prior use of any inhaled corticosteroids (Yes, No)

In addition, data listings will also be provided for:

- Informed consent

- Inclusion/Exclusion criteria violation for subjects with any such violations

